### Participants

The participants in this study will be UCLA Health physicians who complete a pre-op visit for at least one patient undergoing cataract surgery at UCLA in the 12 months prior and 12 months after the study start date and all patients who are seen during such visits.

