### Inclusion Criteria

All UCLA Health physicians perform a pre-op visit for a patient undergoing cataract surgery in the 12 months prior to the study start date as well as all physicians are anticipated to complete such a visit during the 12-month study period. In 2019, 322 physicians at 74 unique UCLA Health clinics performed such a visit. These physicians conducted a total of 1122 pre-op visits for 995 unique patients. To identify patients who presented for a pre-op visit within 30 days of cataract surgery, we used Surgical Consult Encounter Code 2100 in combination with one of four codes used to identify cataract surgery (3470, 2135, 4040, 4263).

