## Statistical Analysis Plan

### Randomisation Strategy

The study statistician will randomise eligible physicians to one of the two study arms. The randomisation will be stratified by the number of pre-op encounters conducted in the pre-intervention period (0, 1–2, 3–5,>6) to ensure appropriate control of physician's experience or preference to conducting pre-op testing.

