### Primary and secondary outcome analysis

We will measure and compare rates of testing in the 12 months before and 12 months after initiation of the randomisation (primary outcome) to determine whether the EHR-based intervention is successful in changing physician behaviour. We will also compare each of the three intervention arms and the usual care arm and will perform exploratory comparisons between nudge 1, nudge 2 and nudge 3 (secondary outcome) to determine whether certain behavioural economic framing techniques are more effective than others at reducing pre-op testing.

Other secondary outcomes will include the percentage of patients who received specific categories of pre-op tests including labs, EKGs and CXRs, same-day surgery cancellations and physician-level

experience measured by the surveys. We will also estimate cost savings associated with the intervention (described below). Evaluation of the primary and secondary outcomes will be performed using generalised linear mixed-effects models at the patient level. We will investigate the impact of all nudges versus control, which will require a threefold correction. As a secondary analysis, we will conduct pairwise comparisons of the nudges. Models will include fixed nudge 1, nudge 2 and Nudge 3 effects, a fixed study period effect (postnudge intervention vs prenudge intervention), second-order interactions between these effects, a fixed stratum effect (hospitalist vs PCP) and random physician effects. Physician effects will account for clustering of patients by physician. Comparisons between changes in utilisation rates across study arms will be estimated and tested using model contrasts. All pairwise comparisons of changes between study arms will be performed to identify the most effective nudge, and Bonferroni corrections will be applied to control the familywise type I error rate at 5%. Intervention effects will be summarised using ORs, 95% CIs and p values (with multiple comparison corrections). Differences between strata will be similarly summarised.

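### A shared pre-period testing rate would estimate the same nudge contrasts with less variance than the planned difference in changes (optional; the size of the gain depends on an unstated ICC)

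*Combined protocol and SAP*

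**What the plan says.** The section on primary and secondary outcome analysis defines the primary outcome through "rates of testing in the 12 months before and 12 months after initiation of the randomisation (primary outcome"). The mixed model is specified as "Models will include fixed nudge 1, nudge 2 and Nudge 3 effects, a fixed study period effect (postnudge intervention vs prenudge intervention"), plus second-order interactions, a hospitalist/PCP stratum effect and random physician effects. Inference is on the interactions: "Comparisons between changes in utilisation rates across study arms will be estimated and tested using model contrasts". Patient covariates are added to the model.

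The same section says the investigators "will perform exploratory comparisons between nudge 1, nudge 2 and nudge 3 (secondary outcome"), but it also plans all pairwise comparisons, Bonferroni-corrected, to find the most effective nudge.

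Under Randomisation Strategy, "The randomisation will be stratified by the number of pre-op encounters conducted in the pre-intervention period", in four groups including zero. These volume groups are not named in the model.

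The analysis population is described in two ways. Participants refers to physicians with a visit "in the 12 months prior and 12 months after the study start date". Inclusion Criteria takes in physicians with a visit in the prior year, and adds that "all physicians are anticipated to complete such a visit during the 12-month study period".

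**The concern.** Physicians are randomised, and no nudge is active in the 12 months before. If physicians are analysed as randomised, every arm therefore has the same expected pre-period rate. The planned model does not use this. It gives each arm its own pre-period level and then removes the estimated difference in full through the arm-by-period terms. With few visits per physician, that estimated difference is mostly noise, and the noise passes into every treatment contrast.

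What is at stake is precision. It matters most if the true effect is smaller than planned, and in the comparisons among nudges. The Power section assumes the same effect in each intervention arm, so nothing in the plan sizes those comparisons.

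**Working it through.** **Inputs.** For 2019, Inclusion Criteria reports 322 physicians, and "These physicians conducted a total of 1122 pre-op visits for 995 unique patients". So m = 1122/322 = 3.48 visits per physician-year. The baseline rate is 65% (Power). The planned effect is read as percentage points, because 90 − 31 = 59 and half of that is 29.5, stated as 30; this gives 65% to 35%. The test level is 0.05/3 for nudge versus control, with two-sided tests assumed. All pairs of four arms number 4 × 3/2 = 6. The documents state no ICC, sample size or power, so there is no planned figure to reproduce.

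**Closed form** (physician means, equal volumes, stable physician effect). The pre/post correlation is r = m·ICC/(1 + (m − 1)·ICC). The variance of a difference in changes is proportional to 2(1 − r), and with a shared pre-period mean it is proportional to 1 − r². The ratio is (1 + r)/2, so the reduction is (1 − r)/2. For example, at ICC 0.10, r = 0.348/1.248 = 0.279 and the reduction is 0.721/2 = 36%.

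**Simulation.** Logistic random-intercept models were fitted with 400 replicates in each of 24 scenarios. Volumes were equal or skewed, and one pattern had 29% of physicians without a pre-period visit. The 65% and 35% were taken either as population rates or as the rates of a typical physician.

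| ICC | r | Reduction, closed form | Reduction, simulation |
|---|---|---|---|
| 0.05 | 0.155 | 42% | 35-46% |
| 0.10 | 0.279 | 36% | 31-39% |
| 0.20 | 0.466 | 27% | 24-29% |
| 0.40 | 0.699 | 15% | 10-19% |
| 0.50 | 0.777 | 11% | not run |
| 0.70 | 0.890 | 5.5% | not run |

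A 10% reduction needs r = 0.8, which is an ICC of about 0.53 with equal volumes and about 0.45 with skewed ones. A separate simulation at a latent-scale ICC of 0.52 gave 5%. On the standard error scale, 10% and 45% become 1 − √0.90 = 5% and 1 − √0.55 = 26%.

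**Same target.** Mean bias was at most 0.04 log-odds in both models. With a stable physician effect, null rejection at a nominal 5% was 4.5-5.2% (planned) and 4.7-5.8% (shared).

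**Power, planned versus shared**, ranges over ICC 0.05-0.4 and the volume patterns:

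| Contrast | Population rates | Typical-physician rates |
|---|---|---|
| 65% to 35%, 0.05/3 | 99-100% vs 100% | 87-99% vs 92.5-100% |
| 65% to 45%, 0.05/3 | 79.5-97% vs 94-98.5% | 51-81% vs 59-99% |
| 35% vs 50%, 0.05/6 | 47-66% vs 66-79% | 17-47% vs 24-78% |

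The 35% versus 50% contrast is an illustration, not a planning value. A 15-point effect (65% to 50%) on population rates gave 52-83% versus 72-89%. At 35% versus 45%, with sixfold correction, both models are weak (15-28% versus 27-37%).

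**Drift.** If physicians change differently between periods (SD 0.7 or 1.0 on the logit scale) and only a random intercept is fitted, null rejection at a nominal 1.67% was 7.0% and 12.2% for the planned model, and 5.9% and 10.1% for the shared-rate model.

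**The case against.** The strongest reply is that the plan's choice is coherent: the outcome is framed as change, the contrast is unbiased, and power at the planned effect is high under either model. That stands, and it is why the point is optional.

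The second reply concerns size. The gain rests on an assumed ICC. Study Intervention says ordering reflects each provider's experience and preferences, so habits may be persistent and the gain small. The volume is from 2019, whereas the pre-period is the year before a June 2021 start, whose volume is not stated. The simulations also omit the volume strata, the hospitalist/PCP term and the patient covariates, so they do not describe the exact model recommended. All of this stands and is why the range is conditional.

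The third reply concerns robustness. In an open-label trial, if the analysis set is selected on post-period activity that differs by arm (one reading of Participants), pre-period rates could differ between the analysed arms. The planned contrast absorbs such differences; the shared rate does not. The alert fires only once a test order is begun at a visit, which limits such selection but does not exclude it.

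Two stronger readings should be resisted. A reader might infer that the planned analysis is biased or wrong; nothing in the documents supports that. A reader might also infer that the zero-visit stratum is a major source of the loss. The documents do not give its size, and the simulations do not bear this out: on population rates, the shared/planned variance ratios were 0.61, 0.65, 0.71 and 0.84 with 29% such physicians, against 0.54, 0.61, 0.71 and 0.85 with none.

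**Conclusion.** The point holds as an optional improvement, with medium confidence. Randomisation justifies a shared pre-period rate, and using it lowers the variance of the same contrasts. The reduction is about 10-45% if the ICC lies between 0.05 and 0.4, the physician effect is stable and volumes resemble 2019. It falls below 10% above an ICC of about 0.5.

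The planned tests are valid if the random physician effects capture the clustering. Under unmodelled drift both models are anticonservative, so a shared rate does not cure that problem. The primary nudge-versus-control conclusion at 65% to 35% is not at risk. Nor should a reader conclude that the change makes the nudge-versus-nudge comparisons adequately powered; in many of the scenarios it does not.

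**What to change.** In the section on primary and secondary outcome analysis:

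- Drop the three arm main effects. Keep the period and arm-by-period terms, the random physician effects and the planned covariates. Each nudge effect is then the post-period log-odds difference from usual care, given a common pre-period rate.
- Add the volume strata used in the randomisation.
- State that all randomised physicians with outcome data are analysed as randomised, without requiring visits in both periods. Bring Participants, Inclusion Criteria and the zero-visit stratum into line with this.
- Keep the planned difference-in-changes contrast as a sensitivity analysis. It guards against pre-period differences created by selection on post-period activity.

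The cost is SAP wording and no new data: three arm terms go out and three stratum terms (four strata) come in. The price is reliance on the as-randomised analysis set.

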### Power

Preliminary analyses of UCLA Health data show that the baseline rate of testing is 65%. In a prior quality improvement study conducted at a different health system, we reduced pre-op lab testing by 59% (a reduction from 90% to 31%). We conservatively estimate an effect half as large (30%) in each intervention arm.

To calculate savings from reduced use of medical services, we will multiply the estimates of utilisation (ie, quantity) for each of the pre-op services measured by the relevant payment rates for the services based on the coverage type for the patient (ie, Medicare and average commercial payment rates per service). We will then compare differences in spending overall and by specific services (ie, lab testing, EKGs) between the control arm and each of the intervention arms and a pooled estimate of the three-nudge intervention arms. We will disaggregate the savings to measure the amount and proportion accrued by the health system/payer versus the patient. An extension of this analysis will estimate how reducing the utilisation of pre-op testing affect different parties; we will disaggregate the savings estimates by type of payer contract (ie, capitated vs fee-for-service(FFS)) to derive estimates of savings to the health systems versus the payer. Under capitated payments, the savings accrue to the health system, while under FFS payments, the savings accrue to the payer and represent revenue losses for the health system.

We will extrapolate observed saving estimates to compute savings the Medicare FFS programme might expect to accrue if similar reductions in the utilisation of pre-op services for cataract surgery were observed in the Medicare population. To generate these savings estimates, we will compute the number of Medicare patients undergoing cataract surgery in a single year and the fraction of patients who have these pre-op tests. We will then take our estimates of reduction in utilisation and apply these estimates to the current use of pre-op testing utilisation in the Medicare FFS programme to determine the number

of services that would be reduced. We would then apply FFS payment rates to the number of services that would be reduced to estimate savings to Medicare. Finally, we will develop estimates of longer term savings in a year–year time range, applying a discount rate to costs, assuming that the observed reduced amount of services used remained similar after the 1-year study period ended.

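### Does the shared word utilisation force one count of tests to serve both the physician-behaviour question and the savings estimate?

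*Combined protocol and SAP*

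**What the plan says.** The Study Objectives hypothesise fewer tests ordered by physicians, and under Study Intervention the alert fires on the visit physician's own order. In Primary and secondary outcome analysis, the primary outcome is the rate of testing in the 12 months before and after randomisation starts, and its purpose is "to determine whether the EHR-based intervention is successful in changing physician behaviour". The secondary outcomes include "the percentage of patients who received specific categories of pre-op tests including labs, EKGs and CXRs" and "same-day surgery cancellations". One sentence then covers the method for all of them: "Evaluation of the primary and secondary outcomes will be performed using generalised linear mixed-effects models at the patient level". A later sentence in the same paragraph adds: "Comparisons between changes in utilisation rates across study arms will be estimated and tested using model contrasts".

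The savings analysis is printed under Power. For the trial itself, "we will multiply the estimates of utilisation (ie, quantity) for each of the pre-op services measured by the relevant payment rates", and spending is then compared between usual care, each nudge arm and the three nudge arms pooled. For Medicare, the base is "the fraction of patients who have these pre-op tests", and "We will then take our estimates of reduction in utilisation and apply these estimates to the current use of pre-op testing utilisation".

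The text of all three nudges (Three Intervention Arms) says that PEPC will order the labs needed on the day of surgery. The Control Arm section says usual-care physicians receive no alert or guideline information. None of these sections states whose orders count or whether day-of-surgery labs count. The appendix with the test list is not in the text available for this review.

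**The concern.** The two questions need different counts wherever PEPC orders labs. A PEPC lab is not the visit physician's decision, but the patient has it and someone pays for it. The plan uses one noun, utilisation, for the model contrasts and for the savings input. It also builds into the nudge arms alone a message that could lead a physician to leave a lab to PEPC.

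Two errors then seem possible. If only visit-physician orders are counted, a lab that moves to PEPC is scored as avoided, and both the lab outcome and the savings look too good. If all orders are counted, the contrast meant to show physician behaviour includes labs from a team that is not described as randomised or alerted, and the effect is diluted. The Medicare extrapolation would carry the first error outside the trial.

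**Working it through.** **The plan's own figure.** Power cites a fall from 90% to 31% in an earlier study: 90 − 31 = 59 points. Half is 29.5, which the plan gives as 30%. From the 65% baseline this means 35% if the 30% is in points (65 − 30), or 45.5% if it is relative (65 × 0.70). Both readings are carried below. The 65% is an overall testing rate; applying it to labs is an assumption.

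**Case (a): savings based on visit-physician orders only.** Let d be the share of avoided labs that PEPC then orders. The documents do not give d. At equal unit price, the overstatement is 1/(1 − d) − 1. Visits in the nudge arms, on the 2019 volume in Inclusion Criteria and an assumed equal split, are 1122 × 3/4 = 841.5. Visits scored as avoided are 841.5 × 0.30 = 252 (points) or 841.5 × 0.195 = 164 (relative), if every avoided visit is treated as a lab visit.

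| d (assumed) | Savings overstated | Shifted visits, points | Shifted visits, relative |
|---|---|---|---|
| 0% | 0% | 0 | 0 |
| 5% | 5% | 13 | 8 |
| 10% | 11% | 25 | 16 |
| 20% | 25% | 50 | 33 |

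**Case (b): behaviour contrast based on all orders, with no shift.** Let q be the share of patients with a PEPC lab, equal in all arms and independent of the physician's order. The documents do not give q either. The percentage tested is 1 − (1 − p)(1 − q). For q = 10% on the points reading: usual care 1 − 0.35 × 0.90 = 68.5%, nudge 1 − 0.65 × 0.90 = 41.5%, difference 27 points. The odds ratio is (0.415/0.585)/(0.685/0.315) = 0.33.

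| q (assumed) | Points: difference, OR | Relative: difference, OR |
|---|---|---|
| 0% | 30.0, 0.29 | 19.5, 0.45 |
| 5% | 28.5, 0.31 | 18.5, 0.46 |
| 10% | 27.0, 0.33 | 17.6, 0.48 |
| 20% | 24.0, 0.36 | 15.6, 0.50 |

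These odds ratios are unadjusted and ignore the random physician effect.

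**Does either case follow from the plan?** Three checks say it does not.

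1. *One count can serve both uses when nothing shifts.* Suppose each arm has k PEPC labs per patient, and physicians order A labs per patient in usual care and B in a nudge arm. The difference over all orderers is (A + k) − (B + k) = A − B, the same as for physician orders alone. The d = 0 row shows this. For quantities and spending within the trial, PEPC ordering as such does no harm; a differential shift is needed, and no section shows one.
2. *The plan does not say that one set of estimates is used twice.* The contrasts concern rates from patient-level models, summarised as odds ratios. The savings input is glossed as a quantity for each service, multiplied by a price, with its own between-arm comparison of spending. That gloss does not settle who ordered the test, but it does show a separate calculation.
3. *Each phrase, read in its place, selects a suitable count.* The primary outcome is tied to physician behaviour, so visit-physician orders are the natural count and case (b) does not arise. The lab outcome is what patients received, and the savings concern use of services; both ordinarily cover any orderer, so case (a) does not arise. For the received outcome, the smaller differences in the second table would be the true answer to its own question.

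**The case for a change.** The strongest case for acting is that the plan leaves the orderer and the window unstated, in a trial whose alert names a second ordering route in the nudge arms only. If utilisation ordinarily covers all orderers, the contrast sentence read literally is not about the visit physician's orders. Without PEPC labs tabulated by arm, the trial also could not show that shifting was absent, which would support its own savings claim. The cost is small: a few sentences, plus orderer and order date from the electronic record that is already the data source.

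Part of this stands. The definition is missing, and a descriptive table of PEPC labs by arm would be a reasonable extra. The Medicare step also needs the reduction and the base to be on the same count if a relative reduction is applied. On the points reading with q = 10%, physician orders alone give 30/65 = 46%, against 27/68.5 = 39% for all orders.

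The literal reading of the contrast sentence does not stand. That sentence sets the method for several outcomes, each already worded for itself, and a generic noun there does not redefine the primary outcome. The all-orderer count has a price too: it brings in unrelated care and dilutes contrasts based on it. Nor does any section say that the necessary labs PEPC would order are the same as the routine tests the alert discourages.

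**Conclusion.** No change to the plan follows. It is true that the plan does not state whose orders count or whether day-of-surgery labs count. This is a gap in detail, limited to labs, that analysts can fill from the stated purpose of each outcome: visit-physician orders for behaviour, any orderer for tests received and for savings.

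A material error needs two things together: savings built on visit-physician orders alone, against the ordinary sense of the wording, and an alert-driven shift of labs to PEPC. Lab savings would then be overstated by 5% to 25% for assumed shifts of 5% to 20%, and by nothing at zero shift. The dilution of the behaviour contrast, from 30 to between 28.5 and 24 points for an assumed PEPC share of 5% to 20% (points reading), needs the all-orderer count to be used for a physician-behaviour outcome, which the plan does not say. Both the shift and the PEPC share are assumptions and may be zero. The primary outcome, read as the visit physician's orders, is not shown to be biased. The unseen appendix could add detail, but a list of tests by procedure code would not by itself identify the orderer.

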# Study Protocol

## Study Objectives

Our first aim is to integrate three distinct 'nudge' alerts into the UCLA Health EHR. Each nudge will test a different behavioural economics framing strategy. Our second aim is to conduct a four-arm randomised pragmatic trial to compare the effectiveness of the nudges to each other and to usual care. We hypothesise that exposure to the nudges will result in a reduction of pre-op tests ordered by physicians. We will randomise providers who conduct pre-op visits for patients with cataract surgery to one of four study arms: nudge 1, nudge 2, nudge 3 or no nudge (usual care) and measure the effect of the intervention on pre-op testing (see below).

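### Does applying Bonferroni to all pairwise comparisons between study arms conflict with the threefold correction for nudges versus control?

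*Combined protocol and SAP*

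**What the plan says.** All of the multiplicity text is in the SAP section Primary and secondary outcome analysis. It first describes the between-nudge work as exploratory: the trial "will perform exploratory comparisons between nudge 1, nudge 2 and nudge 3 (secondary outcome"). It then sets the rule for the main question: "We will investigate the impact of all nudges versus control, which will require a threefold correction". The next sentence places the nudge pairs below that: "As a secondary analysis, we will conduct pairwise comparisons of the nudges". After the model description comes the sentence at issue: "All pairwise comparisons of changes between study arms will be performed to identify the most effective nudge, and Bonferroni corrections will be applied", with a familywise type I error rate of 5% as the target. Results are to be given as follows: "Intervention effects will be summarised using ORs, 95% CIs and p values (with multiple comparison corrections").

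Study Objectives counts usual care among the arms, since physicians go to "one of four study arms: nudge 1, nudge 2, nudge 3 or no nudge (usual care"). The plan states no Bonferroni divisor for the later sentence and does not list the comparisons in its family.

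**The concern.** Four arms make six pairs. If the later sentence means all six as one family, Bonferroni requires 0.0083 for each, and three of those six are the nudge-versus-control contrasts that the plan has already set at 0.0167. The trial's main question would then have two significance thresholds, one twice the other. A result with a p value between them could be called positive or negative depending on which sentence the analyst followed, and in an open-label trial one would not want that choice left until the data are in. If instead 0.0167 were used for all six pairs, the error rate over the six would exceed 5%.

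**Working it through.** **Inputs.** Familywise 5%, the threefold correction and four arms come from the plan. Two-sided tests are assumed, because sidedness is not stated. The baseline testing rate of 65% and the 30% effect come from the Power section. The 1122 visits by 322 physicians in 2019 come from Inclusion Criteria. The documents give no intracluster correlation (ICC) and no figure for how many physicians contribute visits in both periods, so both are treated as assumptions with a range.

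**Thresholds.**
- Three comparisons: 0.05/3 = 0.0167, z = 2.394. This reproduces the plan's threefold correction, since 3 × 0.0167 = 0.05.
- Six comparisons: 4 × 3/2 = 6 and 0.05/6 = 0.0083, z = 2.638. The divisor is inferred.
- Adjusted intervals would be 98.33% or 99.17%. The width ratio on the log-odds scale is 2.638/2.394 = 1.10.

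**Error rate with no true differences** (simulation of four arm changes with equal variance, 4 million draws):

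| Tests | Level per test | Chance of any false positive |
|---|---|---|
| 3 nudge vs control | 0.0167 | 4.4% |
| 3 nudge vs nudge | 0.0167 | 4.4% |
| All 6, one family | 0.0083 | 4.2% |
| All 6, pooled | 0.0167 | 7.8% |

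The first two rows together are the two-family reading, and the third row is the six-pair reading. Each meets 5% for the family it defines. The last row pools a primary family with a secondary one, and the plan does not claim 5% for that pool at 0.0167.

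**How often the choice of threshold would matter.** The contrast is the difference in change of log-odds between a nudge arm and control. Take n = 1122/4 ≈ 280 visits per arm per period, control steady at 65%, and testing rate p in the nudge arm after the intervention:

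SE = √{D × [3/(280 × 0.65 × 0.35) + 1/(280 × p × (1 − p))]}, where D is the design effect.

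With p = 0.35 (a 30-point fall) and D = 1: the effect is 1.238, SE is 0.251 and z = 4.94. Power is Φ(4.94 − 2.394) = 99.5% at 0.0167 and Φ(4.94 − 2.638) = 98.9% at 0.0083.

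With p = 0.455 (a 30% relative fall) and D = 1: the effect is 0.800, SE is 0.248 and z = 3.22. Power is 79.7% and 72.1%.

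**Design effect.** Mean visits per physician are 1122/322 = 3.48. For a before-after contrast, D depends on how many physicians appear in both periods. With equal clusters and no physician-by-period effect, as in the plan's model, and on the linear scale:
- No overlap: D = 1 + (3.48 − 1) × ICC. At ICC 0.20 this is 1.5, and at ICC 0.40 it is 2.
- Full overlap: the physician effect cancels in the change, so D = 1 − ICC. At ICC 0.20 this is 0.80.
- Half overlap at ICC 0.20: (0.80 + 1.50)/2 = 1.15.

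| p after | D | Power at 0.0167 | Power at 0.0083 | Any of 3 contrasts between thresholds |
|---|---|---|---|---|
| 0.35 | 0.80 | 99.9% | 99.8% | 0.3% |
| 0.35 | 1 | 99.5% | 98.9% | 1.5% |
| 0.35 | 1.15 | 98.7% | 97.6% | 3.1% |
| 0.35 | 1.5 | 95.0% | 91.9% | 8.6% |
| 0.35 | 2 | 86.4% | 80.4% | 16.5% |
| 0.455 | 0.80 | 88.7% | 83.3% | 15% |
| 0.455 | 1 | 79.7% | 72.1% | 20% |

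The last column comes from simulating the three contrasts with their shared control arm.

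**The case for a change.** The literal reading is not far-fetched. Study Objectives counts usual care as a study arm. The sentence just before the disputed one speaks of changes across study arms and must include control, since it introduces the contrasts that test the nudges. When the plan means only the nudges, it tends to say so. A programmer could reasonably code six contrasts with a divisor of 6. One sentence in the SAP would settle it, and if 30% is a relative fall the chance that the choice matters for at least one contrast is not negligible.

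Three things stand. The wording is loose, the divisor is not stated for the later sentence, and the intervals are not labelled adjusted or unadjusted. What does not stand is that the main threshold is open. The threefold correction is stated specifically for nudges versus control, and the next sentence makes the nudge pairs secondary. The later sentence gives its own purpose, finding the most effective nudge, which is a between-nudge question. Even if all six pairs are run for that purpose, a general sentence about ranking nudges does not displace the specific rule for the main comparison. The larger between-threshold chances at a 30-point fall (8.6% and 16.5%) also require that no physician appears in both periods. The plan enrols on visits in the 12 months before the start as well as on anticipated visits, and it fits random physician effects across both periods, so some overlap is expected.

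**Conclusion.** This is a gap in wording that analysts fill sensibly, and no change to the plan is needed. The two rules conflict only if the later sentence is read as one family of six. On the natural reading there are two families of three, each at 0.0167 with error about 4.4%, and the nudge-versus-control threshold is the one the plan states. A rewrite would set down the plan's own threefold rule and leave every error rate where it is. Moving to a step-down method such as Holm would gain some power but give up simple matching intervals, in a plan that reports intervals.

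At a 30-point fall, the chance that the choice of threshold decides any nudge-versus-control result is about 0.3% to 1.5% with full physician overlap (ICC 0.20) or independent visits. It rises with little overlap and a high ICC. If 30% is a relative fall it is about 15% to 20% under the same assumptions. These figures assume 2019 visit volumes split equally, two-sided tests and an unchanged control rate.
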